If eligible based on the MDD Phone Screen, parents will receive several forms (BRIEF, ERC, My Child, Emotion Understanding Parent Questionnaire, BIS/BAS, Contact Information, Teacher Contact Information) in the mail or if families have internet access via REDCap to complete before the laboratory assessment. This will take approximately 1 hour to complete. A copy of the Consent Form and Consent Letter will be included in this take-home packet (sent via mail or email). At the Post 1 & Post 2 assessments, parents will receive this packet/REDCap link (BRIEF, ERC, My Child, Emotion Understanding Parent Questionnaire) prior to the in-office assessment to complete on their own.

-IN-OFFICE:

Parent and child will complete the Parent Child Interaction - DPCIS as well as Teaching Tasks (marble maze, etch-a-sketch, and prohibited toys) at Baseline, Teaching Tasks (magnet puzzle, team drawing and prohibited toys) at Post 1 and Waiting Task at Post 2. The PCI will be video recorded and take approximately 45 minutes to complete.

Then, a research team member will assist the child in completing Handedness, Height & Weight measurement, FACE - Blurry Face & Emotion Labeling, KIDSEDF, Emotion Understanding, KBIT-2, Narratives, Dot Probe task, Narratives for Suicidal Ideation, and Death Interview. All these tasks will be video recorded and take approximately 1.5-2 hours.

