TREATMENT (Immediate Treatment Randomization: ~Week 1-18 or Wait List Randomization: ~Week 18-36) During the treatment, parent and child will work with a therapist at the Early Emotional Development Program each week for 18 weeks. Each session will last approximately 1 hour, although there are a few weeks when sessions will last approximately 1.5-2 hours. During these sessions, parent and child will work with a therapist to improve their relationship, learn safe and effective disciplinary techniques, as well as both learn strategies to deal with a range of emotions. (See attached Sessions Manual) The therapist will assign homework and activities on a weekly basis. Parents will complete the ECBI prior to each session. Therapists will complete the DPICS, EDCI, TIC, OC-YC Screener, and Acceptance Inventory throughout the course of treatment.

INTERVAL A, B, C & D ASSESSMENTS (~ Weeks 6, 12, 24, 30) Either over the phone, at the Early Emotional Development Program, or via REDCap, parents will complete the HBQ-P Peer & Medication section, CBCL, PFC-Scale, BDI, PSI, CCNES and TAI. This will take approximately 1-1.5 hours to complete.

DISCONTINUATION

If at any point in the study the family decides to discontinue their participation, the research team will ask the parent to complete an Exit Questionnaire and potentially the parent and child to complete the Post 1 or Post 2 assessment if families are willing to do so.

LONG TERM FOLLOW UP

After the completion of planned study visits (Baseline, Post 1, and Post 2 assessments), the research team will contact families via phone and/or email with the contact information they provided us. This will be done in order to ensure up-to-date contact information. The research team will update their contact information in the REDCap database for future follow-up studies with this population. Participants can let us know if they would no longer like to be contacted for future studies and we will note that in the REDCap database and cease contact.

PCIT-ED Statistical Analysis Plan

All measures will be collected at pre- and post-treatment assessments (except EI). In addition, the HBQ-P (measuring symptom severity of all Axis I disorders and impairment), PFC-Scale, parent BDI-II, PSI, EDCI (measuring ESL in both groups) and will be collected at the 6- and 12-week assessments in both groups. In the PCIT-ED group, these interval assessments correspond to completion of the CDI and PDI modules.

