So, the relative increase in variance due to missing values is 32%, indicating that $1.32 * 180$ subjects = 238 subjects are required to attain the same power that would be attained in a sample of 180 subjects who all complete the study. In other words, 238 subjects must be enrolled in the study, with 180 completing, to achieve the same power when using multiple imputation as would be achieved if 180 subjects were enrolled and all completed. If multiple imputation were not used, and only complete cases were analyzed, approximately 238 subjects would have to be enrolled to produce 180 complete cases. Thus, multiple imputation is more efficient than complete-case analysis, in addition to avoiding bias due to MAR missingness.

A secondary analytic approach will be to use mixed models on non-imputed data. Mixed models can be used to analyze repeated measures data without discarding subjects with missing data. Mixed models will be used for measures only obtained at pre- and post-assessment and on measures with interval assessments. Analytic approaches for each set of specific aims and hypotheses are detailed below.

Specific Aim 1: To conduct an RCT of an early dyadic intervention for PO-MDD, PCIT-ED, compared to a WL control condition.

Hypothesis 1A: Compared to those randomized to the WL, preschoolers who are first randomized to PCIT-ED will show significantly increased rates of remission, greater reductions in MDD symptoms, and decreases in impairment.

Hypothesis 1B: Compared to those randomized to the WL, preschoolers who are first randomized to PCIT-ED will show significantly greater increases in emotional competence measured by the ability to accurately identify emotions in themselves and others and the ability to effectively regulate intense emotions.

Hypothesis 1C: Compared to those on the WL, parents who are first randomized to PCIT-ED will show significantly greater increases in emotion skill learning (ESL) and reductions in MDD symptoms and parenting stress.

Analytic Approach: Continuous post-assessment scores will be compared between PCIT-ED and WL groups using analysis of covariance, covarying for pre-assessment scores. The stratification variables, gender and externalizing comorbid diagnoses, will also be included as covariates in the models.

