PFC-Scale and PAPA MDD severity sum scores will be used to assess differences in depressive symptoms; HBQ and PAPA impairment scores will be analyzed to determine differences in functional impairment. Differences in emotion regulation (as an executive function) in the two groups will be examined using scores from the BRIEF-P; emotion development will be analyzed using scores from the ERC, Emotion Understanding, FACE, KIDSEDF, and the "Waiting" and "Puzzle" tasks. Post-assessment EDCl, BDI-II, and PSI scores will be compared between PCIT-ED and WL groups to determine differences in increases in Emotion Skill Learning and reduction of parental depressive symptoms and parenting stress.

Rates of remission (defined by 50% reduction in MDD severity and not meeting diagnostic criteria) will be compared in the PCIT-ED and WL subjects using logistic regression.

Interval assessment scores will also be analyzed across PCIT-ED and WL groups in repeated measures mixed models. In these models, repeated measures of PFC-Scale, HBQ MDD and externalizing co-morbidity severity and impairment, PSI and ESL (measured by EDCl) at pre-assessment, 6-week assessment, 12-week assessment, and post-assessment will be compared between the PCIT-ED and WL groups.

In addition to the analyses described above, pre-assessment variables that could possibly be associated with outcome, such as subject age and maternal depression, will be investigated as potential predictors of outcome.

Specific Aim 2: To investigate mediators and moderators of treatment effects.

Hypothesis 2A: Parental emotion skill learning (ESL) will mediate treatment effects. Child depression outcomes will be mediated by parental ESL.

Hypothesis 2B: Parental Emotional Intelligence (EI, a stable trait measured at baseline by MSCEIT) will be a moderator of ESL and child outcome. Parents with higher EI will show better ESL, and as a result, children of parents with high EI will show better outcomes than children of parents with low EI.

Analytic Approach: Parental ESL will be measured with the Emotion Development Coding instrument. This is an itemized assessment of parents' emotion skill learning. Each item is rated as 3=satisfactory, 2=needs practice, or 1=not evident. The total ESL score will be calculated as the mean of these items.

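### The Aim 1 ANCOVA leaves out child age, which costs the child emotion-task comparisons a modest amount of precision, most where no same-task baseline is scheduled

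*Combined protocol and SAP*

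**What the plan says.** The SAP, Specific Aim 1, Analytic Approach, sets the arm comparison: "Continuous post-assessment scores will be compared between PCIT-ED and WL groups using analysis of covariance, covarying for pre-assessment scores". It then adds two covariates: "The stratification variables, gender and externalizing comorbid diagnoses, will also be included as covariates in the models". No other covariate is listed, and age is not a stratification variable.

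Later in the same section, age and maternal depression are taken up apart from the arm comparison: "pre-assessment variables that could possibly be associated with outcome, such as subject age and maternal depression, will be investigated as potential predictors of outcome". The SAP does not say whether a predictor found there could enter the arm-comparison model.

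The child outcomes for Hypothesis 1B include performance tasks: "emotion development will be analyzed using scores from the ERC, Emotion Understanding, FACE, KIDSEDF, and the" Waiting and Puzzle tasks. Emotion Understanding, FACE and KIDSEDF belong to the child battery that the protocol lists for all three assessments. The interaction tasks change by visit. Baseline uses a marble maze, an etch-a-sketch and prohibited toys, followed by "Teaching Tasks (magnet puzzle, team drawing and prohibited toys) at Post 1 and Waiting Task at Post 2". The SAP's opening paragraph reads differently: "All measures will be collected at pre- and post-treatment assessments (except EI", where EI is parental emotional intelligence.

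**The concern.** Scores on emotion-recognition and waiting tasks may well depend on age in preschoolers. If age predicts the post score beyond what the pre-score, gender and comorbidity explain, that variation stays in the error term and widens the interval for the treatment effect. A chance age difference between arms is then removed only as far as the pre-score carries it.

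A separate predictor analysis does not help the arm comparison. Because its variable list is open-ended, it also leaves unclear whether the comparison model could be revised afterwards. The SAP states no power or precision for the 1B outcomes, so nothing shows how much residual variance they can bear.

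**Working it through.** **Inputs from the documents.** 90 completers per arm; for MDD severity change, a difference of 2.5 and SD of 4.69, with one-sided alpha 0.05 and stated power 0.97 (SAP, Power for Mediation). No correlation between age and any outcome is given, and no pre-post correlation. Those below are assumptions.

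**The plan's own figure.** SE = 4.69 × √(2/90) = 0.699, and 2.5/0.699 = 3.576. One-sided: 3.576 − 1.645 = 1.931, power 0.973, which agrees with 0.97. Two-sided, the same inputs give 0.947. This figure concerns MDD severity, not the child tasks.

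**Precision with a same-task pre-score.** Let age correlate a with both pre and post scores, and let b be the pre-post correlation. For simplicity, take age as unrelated to gender and comorbidity. The partial correlation of age with the post score, given the pre-score, is

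r = (a − ab) / √[(1 − a²)(1 − b²)].

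Adding age multiplies the residual variance by (1 − r²). The equivalent number of extra completers is 180/(1 − r²) − 180.

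| a | b | r | variance cut | extra completers |
|---|---|---|---|---|
| 0.3 | 0.5 | 0.182 | 3.3% | 6.1 |
| 0.3 | 0.6 | 0.157 | 2.5% | 4.6 |
| 0.3 | 0.7 | 0.132 | 1.7% | 3.2 |
| 0.3 | 0.8 | 0.105 | 1.1% | 2.0 |
| 0.5 | 0.5 | 0.333 | 11.1% | 22.5 |
| 0.5 | 0.6 | 0.289 | 8.3% | 16.4 |
| 0.5 | 0.7 | 0.243 | 5.9% | 11.3 |
| 0.5 | 0.8 | 0.192 | 3.7% | 6.9 |

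The range is about 1% to 11%, or 2 to 22 completers.

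**Precision with no same-task pre-score.** Here r = a. With a = 0.5 the cut is 0.5² = 25%, equivalent to 180/0.75 − 180 = 60 completers.

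**In terms of power.** Take an outcome with 80% two-sided power at 90 per arm, d = (1.960 + 0.842) × √(2/90) = 0.418. Adding age raises power to 80.4%, 81.6% and 83.6% for r = 0.1, 0.2 and 0.3, and to 89.9% for r = 0.5. For the MDD severity inputs, two-sided power moves from 0.947 to between 0.949 and 0.963 for r = 0.1 to 0.3.

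**Chance imbalance.** Without age in the model, the part of the arm difference due to chance age imbalance has SD r√(2/90) in residual-SD units. The 95% range, ±1.96 × r√(2/90), is ±0.03, ±0.09 and ±0.15 for r = 0.1, 0.3 and 0.5.

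**Simulation** (3,000 trials per setting, 90 per arm, a = 0.5, b = 0.6). At d = 0.35:

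- with the pre-score in the model, power is 0.83 without age and 0.86 with it;
- with no pre-score, power is 0.65 without age and 0.77 with it.

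At d = 0, rejection rates are 0.049 to 0.054 across the four models. Mean estimates match the true difference in every case.

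**The case against.** The strongest reply is that the plan already pre-specifies an adjusted comparison and that further covariates are a preference. Much of this stands. The pre-score absorbs a good part of any age effect, and Emotion Understanding, FACE and KIDSEDF each have one. If the scores are age-standardised, which the documents do not say, age may add almost nothing. Even for Puzzle, a score from another baseline teaching task could stand in as a partial pre-score, so 25% is towards the upper end. On the protocol's schedule the Waiting Task falls only at Post 2, so Puzzle is the task that bears on the between-arm comparison at Post 1.

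The SAP also says that all observed variables should inform the imputation, and its simulation included age. That helps predict missing outcomes. It does not adjust the arm contrast for participants who were observed.

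Four stronger readings are tempting and are not supported:

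- *The plan contradicts its own expectation.* The SAP calls age and maternal depression possible, potential predictors. It does not say that they are likely to be prognostic.
- *Chance age imbalance makes the comparison invalid.* Randomization keeps the estimate unbiased on average and type I error at its nominal level. Only precision and the single-trial estimate are affected.
- *The gain is large.* A partial correlation of 0.4 would give a 16% cut, worth about 34 completers (180/0.84 − 180). That lies above the whole range in the table for outcomes with a pre-score.
- *Maternal depression should be added throughout.* Nothing in the documents links it to the child tasks. Since "Post-assessment EDCl, BDI-II, and PSI scores will be compared between PCIT-ED and WL groups" under the same ANCOVA, baseline parent depression is already the pre-score in the BDI-II model. The parent completing the BDI is not stated to be the mother.

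**Conclusion.** The point holds as a minor efficiency improvement for the child emotion-task outcomes, and for age only. Under the assumed correlations, leaving age out forgoes about 1% to 11% of residual variance where a same-task pre-score exists. For Puzzle and Waiting it could forgo up to about 25% if there is no same-task baseline and age correlates 0.5 with the score. The protocol's task schedule and the SAP's statement on data collection disagree on whether that baseline exists, and this decides which figure applies. The documents cannot fix the size more closely. The planned analysis is valid as it stands.

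**What to change.** Add a sentence to the SAP, Specific Aim 1, Analytic Approach: baseline child age enters as a fixed, pre-specified covariate in the ANCOVAs for Emotion Understanding, FACE, KIDSEDF, Puzzle and Waiting. Add a second: the predictor analysis is exploratory and will not alter the arm-comparison model. Parent BDI-II need not be added to the Aim 1 models.

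The protocol's task schedule and the SAP's opening statement should also be reconciled for Puzzle and Waiting, so that it is clear what serves as the pre-score there.

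The cost is one model degree of freedom per ANCOVA and no new data. If the task scores are age-standardised, little or nothing is gained.

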A Randomized Controlled Trial of PCIT-ED for Preschool Depression

NCT02076425

January 13, 2014

PCIT-ED Study Protocol

Parent Child Interaction Therapy Emotion Development (PCIT-ED) will be conducted with a sample of preschoolers who exhibit symptoms of depression compared to a wait list (WL) control after which participants will receive the active treatment. PCIT-ED is an expansion of PCIT, a well-known, widely used and proven effective treatment for preschool disruptive disorders. To address early disturbances of mood and affect, a novel ED module was added based on empirical data in emotion development. The ED module targets parent emotion learning skills with the goal of training the parent to serve as a more effective emotion teacher and coach to the child. The goal of the ED module is to enhance the child's capacity for emotion recognition and regulation or "emotional competence." In order to test the efficacy of PCIT-ED, to estimate accurate effect sizes and to investigate mediators and moderators of treatment response participants will complete comprehensive pre-, interval, and post-assessments.

SCREENING

Prior to screening potential participants, a research team member will obtain verbal consent (see 'Initial Phone Screen'). Once this is complete and the team member answers parents' questions, the PFC (if not already completed) and then Initial Phone/Exclusion Screen will be administered. If team member suspects possibility of an ASD, the SRS will be administered to the parent. If eligible based on PFC and Initial Phone/Exclusion Screen (and possibly SRS), another phone interview will be scheduled and the team will administer the MDD Phone/Inclusion Screen which will be audio recorded. Research staff will utilize Washington University's Research Electronic Data Capture (REDCap) to administer and record information from potential participants. When potential subjects screen-out based on not meeting MDD eligibility criteria, the research team will send the 'PCIT-ED RCT Screen-Out Follow-Up Letter' to inform them of the possibility of re-screening if the child's moods and behaviors worsen.

BASELINE, POST 1 and POST 2 ASSESSMENTS:

-TAKE HOME:

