To assess parental ESL as a potential mediator of the relationship between treatment group and child treatment response, a macro (for SAS or SPSS) developed by Hayes will be utilized. For mediation analyses, the PROCESS macro estimates path coefficients in a mediation model and generates bootstrap confidence intervals for the indirect effects of the independent variable on the dependent variable through a mediator variable. It is also possible to include covariates not proposed to be mediators in the model. Paternal ESL will be evaluated by entering post ESL score into the model as a potential mediator, with treatment group as the independent variable and change in PAPA MDD severity sum score as the dependent variable.

Power for Mediation: To estimate power for this mediation analysis, the following steps were taken. First, we expect the difference in MDD severity sum change score in the two groups to be approximately 2.5, with a SD of 4.69 (based on our pilot study). With 90 subjects per group, an alpha of 0.05, and a 1-sided test, power=0.97. Next, we expect the correlation of change in MDD severity sum score and ESL score to be approximately 0.25. Using Fisher's Z transformation with a sample size of 180, the correlation of 0.25 transforms to $Z = \tanh(0.25) * \sqrt{180-3} = 3.398$. Subtracting 1.96 gives 1.438, corresponding to power=0.92. Thus, we will be well-powered to detect a mediation effect.

To assess parental emotional intelligence (EI) as a potential moderator of treatment response, the PROCESS macro will be used. For moderation analyses, the PROCESS macro

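### The Aim 2A mediation model reads parental ESL and child change at the same visit with no time-ordered term, so it cannot tell whether ESL helped the child or the child's improvement raised ESL

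*Combined protocol and SAP*

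**What the plan says.** - **Hypothesis** (SAP, Specific Aim 2, Hypothesis 2A): "Child depression outcomes will be mediated by parental ESL". The statement has a direction: treatment raises ESL, and ESL lowers child depression.
- **Model** (Aim 2, Analytic Approach): a PROCESS mediation analysis "entering post ESL score into the model as a potential mediator, with treatment group as the independent variable and change in PAPA MDD severity sum", where the change is the dependent variable. The text notes that covariates are possible but names none for this model.
- **Timing of measures** (SAP, opening paragraph): "All measures will be collected at pre- and post-treatment assessments (except EI" being the one exception). The time points of the change score are not spelled out; pre to post is the natural reading. Treatment lasts 18 weeks (Protocol, Treatment).
- **Modules.** The Protocol introduction says "The ED module targets parent emotion learning skills". On the 6- and 12-week assessments, the SAP says "In the PCIT-ED group, these interval assessments correspond to completion of the CDI and PDI modules". No start week for ED is given.
- **Interval data.** The SAP schedules the PFC-Scale at 6 and 12 weeks, and "EDCI (measuring ESL in both groups) and will be collected at the 6- and 12-week assessments in both groups". Under Aim 1 these feed repeated-measures comparisons between groups. Nothing in Aim 2 uses them for mediation, and no lagged or sensitivity analysis for mediation is planned.

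**The concern.** Randomisation protects the path from group to ESL and the path from group to child outcome. It does not protect the path from ESL to outcome, which is an observational association within the trial. When both are read at one visit, that association has the same form whichever of the two moved first. A parent whose child is already calmer may find the emotion skills easier to practise and display.

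The SAP does not limit what a significant indirect effect may be taken to show. At stake is the trial's statement of mechanism, that teaching parents emotion skills is what improves the child. If CDI and PDI end at about weeks 6 and 12, ED occupies roughly the last third of the course. Part of the change credited to ESL could then predate the module meant to raise it.

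**Working it through.** **1. The plan's own figures.** Inputs from Power for Mediation: difference 2.5, SD 4.69, 90 per group, one-sided alpha 0.05, correlation 0.25, N = 180.
- Group difference: power 0.973 (stated 0.97).
- Correlation: arctanh(0.25) × √177 = 3.398, and Φ(3.398 − 1.96) = Φ(1.438) = 0.925 (stated 0.92). The SAP prints tanh, but its 3.398 requires arctanh; tanh gives 3.258 and power 0.903.

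Both figures reproduce. They cover the total effect and a correlation, not the indirect effect, and neither depends on which way the correlation arose.

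**2. How often the planned model declares mediation when ESL does nothing for the child.** Let child improvement produce a within-group correlation of 0.25 with ESL, and let the total group difference in post ESL be d SDs. The documents give no value for d, so a range is shown. The indirect effect is significant roughly when both of its paths are:
- Group to ESL: z = d × √(90/2) = 6.708d, with P_a = Φ(z − 1.96) + Φ(−z − 1.96).
- ESL to change: P_b = 0.925, from step 1.

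| d (assumed) | z | P_a | P_a × 0.925 | Simulated, N = 180 |
|---|---|---|---|---|
| 1 | 6.708 | 1.00 | 0.92 | 0.92-0.95 |
| 0.5 | 3.354 | 0.918 | 0.85 | about 0.85 |
| 0.25 | 1.677 | 0.389 | 0.36 | 0.33-0.38 |
| 0 | 0 | 0.05 | 0.05 | about 0.05 |

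If treatment does not train ESL at all, child improvement alone still moves ESL by 0.25 × 2.5/4.69 = 0.13 SD. The simulated rate is then 0.12.

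**3. Sensitivity to the correlation.** At r = 0.15, arctanh(0.15) × √177 = 2.011, so P_b = Φ(0.051) = 0.52, which is also the rate at d = 1. The SAP does not say whether 0.25 is within-group or pooled over groups. If pooled, part of it comes from the group differences. With 2.5/4.69 = 0.533, the within-group value is 0.25 × √[(1 + d²/4)(1 + 0.533²/4)] − 0.533d/4. At d = 1 this is 0.289 − 0.133 = 0.156, and the rate is about 0.55. At d = 0.5 it is 0.200, and the rate is 0.770 × 0.918 = 0.71.

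**4. Whether adjusting for week-12 symptoms settles direction.** Simulated at d = 1 and r = 0.25, with half the change variance before week 12 (assumed). False mediation with week-12 change as a covariate:
- ESL driven only by change to week 12, measured without error: about 5-7%.
- The same, with week-12 reliability of 0.7 or 0.5 (assumed): about 26% or 51%.
- ESL driven by the whole 18-week change: about 67%.
- ESL driven only by change after week 12: about 100%.

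The adjustment works only for the part of the reverse path that it conditions on.

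**The case against.** The strongest reply is that concurrent mediation is a familiar limit of interpretation in an explanatory aim, and that the high rates rest on an assumed effect on ESL. The second part is correct: without a sizeable effect on ESL the rate is low. But Hypothesis 1C expects parents' ESL to rise, and ED was added to raise it, so a material difference is the trial's own scenario. At d = 1 treatment really does raise ESL; only the ESL-to-child path is false.

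A reader might also infer more than the documents support:
- *That 12 of the 18 weeks precede ED as a matter of record.* This follows only by elimination from the interval visits. The Sessions Manual is not in the text, and nothing says that ESL can move only during ED. The shared-visit problem does not depend on it.
- *That a positive result would be false.* Nothing shows that reverse causation occurs; the planned test simply cannot exclude it.
- *That the week-12 data already scheduled would resolve direction.* Step 4 shows that they would not. Post ESL and post symptoms would still be concurrent. Week-12 status is also a post-randomisation variable that treatment may affect, so conditioning on it changes the quantity estimated.

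**Conclusion.** The concern holds as a limit on what Aim 2A can conclude. The planned model relates post ESL to change ending at the same visit, without baseline ESL or a time-ordered term, and cannot separate the two directions. At the SAP's correlation, read as within-group, it would declare mediation with no ESL effect on the child in about 92-95% of trials at a 1 SD effect on ESL, about 85% at 0.5 SD, 33-38% at 0.25 SD and 5% at 0. At 1 SD this is about as often as the 0.92 power that the SAP quotes for its correlation step. The rates fall if the correlation is weaker or is pooled over groups (about 0.52-0.55 at 1 SD). They illustrate what the test could do and do not predict this trial's result. The Aim 1 randomised comparison is not affected.

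**What to change.** 1. Keep the PAPA mediation model, add baseline ESL and baseline MDD severity as covariates, and state that it reports an association that does not establish direction.
2. In the PCIT-ED-first arm, add a time-ordered analysis: Post 1 ESL predicting Post 2 MDD severity, adjusted for Post 1 severity.
3. Optionally, and as a sensitivity analysis only, model post PFC-Scale adjusted for baseline and week-12 PFC-Scale. State with it that it removes reverse causation only through change up to week 12, depends on the reliability of the week-12 score, conditions on a post-randomisation variable, and still reads ESL and outcome at one visit.
4. Reconcile the ESL schedule before any week-12 ESL covariate is used. The SAP collects EDCI at weeks 6 and 12 in both groups; the protocol's list for Intervals A to D omits it and names it among forms that therapists complete during treatment. The protocol's Baseline and Post lists do not name it either, so confirm the baseline and post scores in both arms at the same time. The PFC-Scale is in both interval lists.

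The cost is SAP wording and a few model runs, with no visit or measure beyond those the SAP schedules. The lagged analysis uses one arm only, is less precise and is not randomised, so unmeasured common causes of ESL and later severity remain possible. The optional model replaces the PAPA score with a parent-completed scale, because PAPA is not listed at the intervals.

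### The Aim 2A mediation model sets the post-assessment ESL level against change in MDD severity and commits to no baseline covariate, so the unrandomized ESL-to-outcome path can be confounded

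*Combined protocol and SAP*

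**What the plan says.** Under Specific Aim 2, Hypothesis 2A is that "Parental emotion skill learning (ESL) will mediate treatment effects". ESL is scored from items rated 1 to 3: "The total ESL score will be calculated as the mean of these items". It is therefore a level at one time point, not a gain.

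The Aim 2 Analytic Approach specifies the model by "entering post ESL score into the model as a potential mediator, with treatment group as the independent variable". For the outcome, the same sentence names "change in PAPA MDD severity sum score as the dependent variable". On covariates it says only "It is also possible to include covariates not proposed to be mediators in the model", which describes the software and commits to nothing.

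Aim 1 is handled differently: "Continuous post-assessment scores will be compared between PCIT-ED and WL groups using analysis of covariance, covarying for pre-assessment scores", with gender and externalizing comorbidity also in the models. That text belongs to Aim 1 and is not carried into Aim 2.

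The SAP does plan the baseline data. Its opening paragraph says "All measures will be collected at pre- and post-treatment assessments (except EI", EI being the one exception, and the Aim 1 repeated-measures models use ESL at pre-assessment, 6 weeks, 12 weeks and post-assessment.

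**The concern.** An indirect effect is the product of two paths. Treatment to ESL is a randomized comparison. ESL to outcome is not: within an arm, parents with high and low post ESL may have differed from the start.

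Two mechanisms matter here.

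- **Existing skill.** Post ESL includes whatever skill the parent brought to the trial. If that skill itself predicts improvement, the model credits it to learning.
- **Dependence of change on baseline severity.** Children must still meet MDD criteria at Baseline to be randomized, so some regression to the mean is expected. If more skilled parents have less severely affected children, those children have less room to improve, and ESL looks less helpful than it is.

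The first can produce apparent mediation where there is none, and the second can hide real mediation. Hypothesis 2A is tested by this one model.

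**Working it through.** **The plan's own figures.** The SAP gives two powers for mediation.

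- Group difference 2.5, SD 4.69, 90 per group, one-sided 0.05: recomputed 0.973, stated 0.97.
- Correlation 0.25, N=180: atanh(0.25) × √177 = 3.398; 3.398 − 1.96 = 1.438; Φ(1.438) = 0.925, stated 0.92. (The text prints tanh, but its value of 3.398 comes from the inverse function.)

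Both reproduce. The 0.25 is a plain correlation, so the power step assumes no baseline adjustment either.

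**Bias in the ESL path when the true effect is zero.** Work in SD units, with negative change meaning improvement. Let ρ be the pre/post ESL correlation, r the baseline ESL-severity correlation, s the slope of change on baseline severity, and g the direct effect of baseline skill on change. Within arms,

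bias = ρ × (s × r + g).

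The documents give none of these four inputs; all values below are assumptions. The rejection columns are simulated two-sided 5% tests of the ESL path, with N=180 and about 3,000 replicates.

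| r | ρ | s | g | Bias | As stated | Both baselines added |
|---|---|---|---|---|---|---|
| 0 | 0.5 | −0.5 | 0 | 0 | 5% | 5% |
| −0.2 | 0.5 | −0.5 | 0 | +0.05 | 10% | 5% |
| −0.3 | 0.5 | −0.5 | 0 | +0.075 | 17% | 5% |
| −0.3 | 0.7 | −0.5 | 0 | +0.105 | 28% | 5% |
| −0.4 | 0.7 | −0.6 | 0 | +0.168 | 62% | 5% |
| 0 | 0.5 | −0.5 | −0.2 | −0.10 | 25% | 5% |
| 0 | 0.7 | −0.5 | −0.2 | −0.14 | 43% | 5% |
| −0.4 | 0.7 | −0.5 | −0.2 | 0 | 5% | 5% |

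Example for the fifth row: 0.7 × (−0.6 × −0.4 + 0) = 0.168. With the simulated standard error of 0.0740, 0.168/0.0740 = 2.27, and Φ(2.27 − 1.974) = 0.62, which agrees with the simulation.

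A positive bias means higher ESL with less improvement, against the hypothesis. A negative bias favours it. In the last row the two mechanisms cancel.

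**Both paths together.** Requiring both paths to be significant, with an assumed treatment effect on ESL of 0.8 SD and s = −0.5, gave false mediation in 5% to 47% of trials unadjusted and about 5% adjusted. The treatment-to-ESL path was 0.80 with or without adjustment.

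**Price of adjustment.** Mean standard errors of the ESL path, unadjusted then adjusted, in rows three to five were 0.0749 and 0.0755 (ratio 1.01), 0.0747 and 0.0916 (1.226), and 0.0740 and 0.0846 (1.14). Applying the largest ratio to the plan's own Z gives 3.398/1.226 = 2.772; 2.772 − 1.96 = 0.812; Φ(0.812) = 0.79. This is illustrative only.

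**The case against.** The strongest reply is that the SAP does not exclude baseline adjustment. It says covariates can be entered, and under Aim 1 it plans to examine pre-assessment variables as predictors of outcome. That stands: a reader might infer that baselines are ruled out, but the text only leaves them unspecified. It does not remove the point. The model that is written down contains three variables, and covariates chosen after the data are seen would not be prespecified.

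Second, a reader might infer that the indirect effect is biased. The documents do not support that. With no relation between baseline ESL and either severity or change the bias is zero, and two opposing mechanisms can offset.

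Third, a reader might take 62% as the rate of false support for ESL mediation. It is not. In that scenario the spurious path runs against Hypothesis 2A, and rejections in its favour are close to zero. The hypothesis-favouring scenarios give about 25-43%.

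Fourth, the SAP would use bootstrap intervals for the indirect effect, while the table tests the ESL path. The joint-significance result (5% to 47%) is a closer proxy and leads to the same conclusion, but the bootstrap itself was not simulated.

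Fifth, the 5% after adjustment follows from the set-up, because the two baselines are the only confounders simulated. This also stands: other unmeasured mediator-outcome confounders would remain.

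**Conclusion.** The point holds as a conditional one. Followed as written, the Aim 2A model leaves the ESL-to-outcome path open to confounding by parents' existing skill and by baseline severity, while the SAP plans the data needed to adjust for both and does so in Aim 1. In the assumed scenarios, false rejection of the ESL path runs from about 5% to about 62%, in either direction, against about 5% with both baselines in the model. The range rests on assumed correlations, so it shows what is possible and does not estimate what will happen in this trial.

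The treatment-to-ESL path, the total treatment effect and the Aim 1 efficacy comparisons are not affected. The change is worth making because Hypothesis 2A depends on this model.

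**What to change.** In the Aim 2 Analytic Approach, name pre-assessment ESL, pre-assessment PAPA MDD severity, gender and externalizing comorbidity as covariates in both mediation equations. The outcome may be post severity or change; once baseline severity is in the model, the ESL coefficient is the same. State that the ESL-to-outcome path still rests on there being no other unmeasured confounding.

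Costs and checks:

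- The standard error of the ESL path may rise by about 0-23%. At the upper end the stated 0.92 power would be about 0.79, so the power statement should be rechecked.
- Confirm that the EDCI is collected at Baseline in both arms. The SAP plans it, but the protocol's Baseline, Post 1 and Post 2 lists do not include it, and the Treatment section has therapists complete it during treatment. These passages need reconciling, particularly for wait-list families. If they can be, the change is to SAP wording only.
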